3 STUDY ENDPOINTS

3.1 Efficacy endpoints:

Radiographic tumor assessments (CT scan or MRI) will be performed by RECIST 1.1. The endpoints of efficacy assessment include:

- ORR described as the proportion of patients who achieve CR or PR by the combination therapy.
- PFS described as the time from study treatment initiation to the date of disease progression or death due to any cause. Patients without progression will be censored at the time of the last follow up.
- OS described as the time from study treatment initiation to the date of death due to any cause. Patients without progression will be censored at the time of the last follow up.

3.2 Safety endpoints:

- Incidence of AEs including but not limited to treatment-emergent AEs, serious AEs, deaths, and clinical laboratory abnormalities, as assessed by the NCI CTCAE v5.0.
- DLT is defined as any of the following adverse reaction observed during first cycle of treatment, and assessed as *possibly*, *probably* or *definitely* related to treatment with copanlisib in combination with fulvestrant. NCI CTCAE v. 5.0 will be used for grading of AEs.

- **Non-hematological AEs:**

- Grade ≥ 2 non-infectious pneumonitis
- Laboratory abnormalities meeting Hy's law criteria (AST or ALT $>3 \times$ ULN with concomitant TB $>2 \times$ ULN). (FDA 2009)
- Any \geq Grade 3 AE, except:
 - Grade 3 fatigue lasting ≤ 5 days
 - Grade 3 nausea or vomiting that has resolved to grade ≤ 2 within 3 days after standard antiemetic therapies
 - Grade 3 diarrhea that has resolved to grade ≤ 2 within 3 days after standard antidiarrheal therapies
 - Isolated laboratory findings not associated with signs or symptoms and lasting less than 3 days, including but not limited to grade 3/4 alkaline phosphatase, uric acid, amylase, and lipase elevations, and grade 3 electrolyte laboratory abnormalities hypophosphatemia, hypokalemia,

Proprietary Information of MD Anderson

Protocol 2020-1241

19 October 2022

hypocalcemia, or hypomagnesemia responsive to supplementation and grade 3/4 lymphopenia.

- Grade 3 hyperglycemia lasting ≤ 7 days

- **Hematological AEs:**

- Grade 4 neutropenia lasting ≥ 7 consecutive days
- Grade 3 and grade 4 febrile neutropenia
- Grade 4 anemia (in the absence of disease progression in bone marrow)
- Grade 3 anemia requiring blood transfusion
- Grade 4 thrombocytopenia of any duration
- Grade 3 thrombocytopenia lasting ≥ 7 consecutive days or associated with bleeding

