- **The following event is classified as a DLT:**

- If a full cycle of copanlisib (3 doses) will not be completed due to any study intervention-related AE, the AE is considered as a DLT
- A delay of over 1 week in initiating Cycle 2 of copanlisib and/or fulvestrant treatment occurs secondary to any study drug related AE, the AE will be considered a DLT
- Death not clearly attributed to underlying disease or alternative cause

Note: Allergic reactions leading to discontinuation of study interventions will not be considered as a DLT and participant will be replaced.

3.3 Exploratory endpoints:

Biomarker-based studies will be performed using tumor tissue and liquid biopsies to assess clonal evolution, and mechanisms of innate and adaptive resistance.

Tumor biopsies, if medically feasible, will be obtained at screening (within 28 days of Cycle 1, Day 1) on-treatment after fulvestrant and copanlisib administration on Cycle 2 Day 1 and at EOT. Biopsies will be optional but encouraged, especially in patients with a response or prolonged disease control. Examples of studies include identification of genomic biomarkers of response and intrinsic or adaptive resistance by whole exome, targeted NGS, and Nanostring DSP or other similar methods.

Proprietary Information of MD Anderson

Protocol 2020-1241

19 October 2022

[figure not shown]
Mandatory blood samples to isolate plasma ctDNA will be collected at pre-treatment (Day -28 to Day1 of Cycle 1), on-treatment (pre-dose -at the same time as the on treatment biopsy- on Cycle 2 Day 1 as well as at the first two restaging visits), and post-treatment at EoT.

Plasma ctDNA samples will be used to evaluate changes in ctDNA quantity and clonal evolution by selected molecular methods that may include targeted NGS, methylation sequencing, and droplet digital polymerase chain reaction.

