5 STUDY POPULATION

5.1 Patient Population

The study population will consist of subjects with selected HR+ (ER+ or/and PR+) advanced or metastatic solid tumors with PI3K (*PIK3CA*, *PIK3R1*) and/or *PTEN* alterations. Patients must have no available standard therapy known to prolong survival or are not candidates for such a therapy.

[figure not shown]

Proprietary Information of MD Anderson

Protocol 2020-1241

19 October 2022

all patients complete the first 28 days, the study will advance to Part 2 (dose expansion), provided there is no more than 1 DLT observed. Patients will be considered evaluable for Part 1 once they have completed at least 1 cycle of treatment or they experience DLTs in the first treatment cycle.

[figure not shown]

Cohort 1: Ovarian cancer (ER+ and/or PR+, PI3K or PTEN altered).

Cohort 2: Endometrial cancer (ER+ and/or PR+, PI3K or PTEN altered).

Cohort 3: Breast cancer (ER+ and/or PR+, PI3K or PTEN altered). Cohort 3 will be enriched to include at least 7 patients naïve to any PI3Ki in Stage 1 and also in Stage 2.

Patients will be considered evaluable for Part 2 once they have completed at least 2 cycles of treatment and have at least one efficacy assessment.

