6.1.1 Copanlisib dosing requirements for pre-dose glucose levels

Copanlisib should be administered if pre-glucose level is <160 mg/dL for fasting, or <200 mg/dL for non-fasting participants. Fasting status refers to a ≥ 8 hours fast. Non-fasting status includes any caloric intake, such as meals, as well as juice, snacks, and other caloric intake not consistently called a meal.

For diabetic participants, who take insulin treatment at any cycle visit, timing and content of meal intake will be managed by the investigator. Consultation with treating physician or endocrinologist is advised.

Because of inhibitory effect on PI3K α -isoform, which is implicated in insulin metabolism, copanlisib infusions may be associated with temporary increase in blood glucose. Addition of a meal in close proximity to copanlisib infusion may exacerbate glucose increase.

On infusion days, a low calorie or low carbohydrate diet is recommended. The timing and content of caloric meal intake and additional glucose testing (if clinically indicated) is managed and monitored by the investigators based on glucose response patterns during prior intervention days. Consultation with endocrinologist is advised.

All glucose measurements done at the site, oral glucose lowering medication and/or insulin administration, if applicable, fasting/non-fasting status and meal intake timing on infusion days will be collected as part of the clinical source documentation.

[figure not shown]
Proprietary Information of MD Anderson

Protocol 2020-1241

19 October 2022

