6.2 Dose Modification

Any toxicity observed during the study can be managed by interruption of the dose of study treatments or dose reductions. Repeated dose interruptions are allowed as required, for a maximum of 4 weeks on each occasion. Where toxicity recurs following re-challenge with study drugs, and where further dose interruption is considered inadequate for toxicity management, then withdrawal is indicated.

[figure not shown]
If either of the study drugs or both drugs need to be held due to AEs, then the study drug deemed to be responsible for the AE will be held until AE resolves to grade 1 or baseline. When copanlisib or fulvestrant dosing is interrupted, either the patient must recover completely, or the toxicity must revert to NCI CTCAE \leq Grade 1 or baseline before restarting study treatment. Patients whose NCI CTCAE Grade 3 or 4 event does not resolve to \leq 1Grade or baseline within 4 weeks should be withdrawn from the study. When a patient withdraws prior to study completion, all applicable activities scheduled for the final study visit should be performed at the time of withdrawal. Any AEs that are present at the time of withdrawal should be followed until \leq Grade 1 or baseline.

Proprietary Information of MD Anderson

Protocol 2020-1241

19 October 2022

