- o) Hematology (CBC with platelet and differential WBC count) will be performed at baseline, weekly (D1, D8, D15, D22) during Cycle 1, twice during cycle 2 (D1 and D15), and then at the start of every cycle thereafter (within 3 days prior to treatment), or more frequently if clinically indicated. Finally at EOT/progression.
- p) Clinical chemistry (total protein, albumin, indirect and TB, AST, ALT, ALP, electrolytes [sodium, potassium, calcium, and magnesium], serum phosphate, serum creatinine, creatinine clearance, uric acid, and bile salts) will be performed at baseline, weekly (D1, D8, D15, D22) during Cycle 1, twice during cycle 2 (D1 and D15), and then at the start of every cycle thereafter (within 3 days prior to treatment), or more frequently if clinically indicated. Finally at EOT/progression.
- q) Mandatory blood samples to isolate plasma ctDNA will be collected at pre-treatment (Day -28 to Day 1 of Cycle 1), on-treatment (pre-dose on the same day as the on treatment biopsy on Cycle 2 Day 1, as well as during the first two restaging visits), and post-treatment at EoT. A maximum of 5 ctDNA samples will be collected per patient.
- r) Tumor biopsies, if medically feasible, will be obtained at Screening (within 28 days of Cycle 1 Day 1), on-treatment after fulvestrant and copanlisib administration on Cycle 2 Day 1 and at EOT. Tumor biopsies will be optional but encouraged, especially in patients with a response or prolonged disease control. Tumor biopsies will be used to evaluate genomic biomarkers of response and intrinsic and adaptive resistance, and to evaluate pharmacodynamic markers of engagement.
- s) Pregnancy tests will be only for women with childbearing potential. Only whole blood will be collected for the pregnancy test that will be performed in the Screening period (Day -28 to Day -1).
- t) Additional pregnancy tests will be performed at Day 1 of each Cycle only for women with childbearing potential. Whole blood or urine can be collected for the test.
- u) Pregnancy test for Cycle 1 Day 1 can be skipped if the test for the screening period is performed close to the 1st cycle.

- v) FPG testing will be performed at Screening and before each copanlisib administration on Day 1, Day 8, and Day 15 of each Cycle from Cycle 1 to Cycle 4 inclusive. Starting with Cycle 5, FPG testing will only be performed on Day 1 of each cycle.

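### In Cycle 1, the DLT window, no glucose is scheduled for 14 days after the Day 15 copanlisib infusion, although the hyperglycemia exception turns on 7 days and blood is already drawn on Day 22

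*Combined protocol and SAP*

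**What the plan says.** Section 3.2 defines DLTs over the first cycle. Among its exceptions to the rule that a related non-hematological event of Grade 3 or higher is a DLT is "Grade 3 hyperglycemia lasting" 7 days or less. The visible text after Section 5.1 lets the study advance to Part 2 "provided there is no more than 1 DLT observed". Section 2.1 makes DLTs part of the Part 1 primary objective.

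The glucose schedule is in Appendix A, footnote v: "FPG testing will be performed at Screening and before each copanlisib administration on Day 1, Day 8, and Day 15 of each Cycle". In the fasting plasma glucose row, Cycle 1 Day 22 is empty. Chemistry is drawn on Day 22, but the panel in footnote p ends with "serum phosphate, serum creatinine, creatinine clearance, uric acid, and bile salts" and nowhere lists glucose.

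Other testing is conditional. Section 6.1.1 leaves additional glucose tests to the investigator, and the end of 6.3.1.1 does the same for home monitoring. Tables 10 and 11 give instructions for raised values once they are found, on the infusion day or later.

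**The concern.** Section 6.5 describes hyperglycemia as very common with copanlisib, so the exception is likely to be needed. Applying it requires knowing when a Grade 3 episode began and whether it was over within 7 days. After the first two infusions, the pre-dose test a week later gives a fixed reading. After the third there is no such reading until the next cycle starts, although the patient attends and gives blood on Day 22.

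What is at stake is the completeness and dating of hyperglycemia in the part of Cycle 1 when the patient has had all three doses. That bears on the Part 1 DLT count and on the duration of treatment-related events and laboratory abnormalities, which Section 8.1 says will be reported. It is also a plain safety-monitoring matter.

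**Working it through.** The plan states no figure on this point, so there is nothing to reproduce. The check is interval arithmetic on the visit schedule.

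**Inputs**
- Scheduled glucose in Cycle 1: Days 1, 8 and 15, before dosing (Appendix A, glucose row and footnote v).
- Next scheduled glucose: Cycle 2 Day 1. With 28-day cycles this is 28 + 1 = Day 29.
- Visit window: ±2 days at treatment visits (Appendix A).
- Duration limit in the exception: 7 days (Section 3.2).

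**Formulas**, for visits at nominal days a and b:
- nominal gap = b − a
- shortest gap = (b − 2) − (a + 2)
- longest gap = (b + 2) − (a − 2)

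**Current schedule**
- Day 1 to Day 8: 8 − 1 = 7 days. Taking Day 1 as the anchor, the range is 6 − 1 = 5 to 10 − 1 = 9.
- Day 8 to Day 15: 15 − 8 = 7 days; range 13 − 10 = 3 to 17 − 6 = 11.
- Day 15 to Day 29: 29 − 15 = 14 days; range 27 − 17 = 10 to 31 − 13 = 18.

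At nominal dates, two of the three infusions are followed by a scheduled glucose within 7 days. The third is not. Its gap exceeds the limit by 14 − 7 = 7 days nominally, and by 10 − 7 = 3 to 18 − 7 = 11 days across the windows. No permitted combination of visit dates brings it within 7 days.

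**With glucose added on Day 22**
- Day 15 to Day 22: 22 − 15 = 7 days; range 20 − 17 = 3 to 24 − 13 = 11.
- Day 22 to Day 29: 29 − 22 = 7 days; range 27 − 24 = 3 to 31 − 20 = 11.

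All three infusions then have a scheduled glucose within 7 days at nominal dates. Late visits can still stretch the gap to 11 days, as they already can between Days 8 and 15.

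**Do the other DLT rules cover the interval?** Section 3.2 also counts an event as a DLT "If a full cycle of copanlisib (3 doses) will not be completed due to any study intervention-related AE". Once the third infusion has been given, that rule can no longer catch a later event. The remaining rule, a related delay of more than one week in starting Cycle 2, catches hyperglycemia that is still preventing treatment around Day 29 and after. Neither rule catches a Grade 3 episode that starts after the Day 15 infusion, lasts more than 7 days, and is resolved or controlled by Day 29.

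**The case against.** The strongest reply is that durations in this trial come from clinical follow-up, not from scheduled draws matched to each limit. Section 7.2 requires onset and resolution dates for each adverse event. Table 10 asks for a repeat laboratory glucose above 250 mg/dL and prompt specialist input for symptomatic or persisting rises. Table 11 covers values noted on later days. Section 6.1.1 makes all glucose values measured at the site, and insulin use, source data. A patient newly started on insulin is unlikely to go 14 days unmonitored. Table 9 describes Grade 3 or higher by intervention, including insulin being started, so treatment records also help to date an episode. Eligibility excludes type 1 and uncontrolled type 2 diabetes and requires fasting glucose of 140 mg/dL or less.

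Most of this stands, and it keeps the point small. What it does not supply is a required glucose at any fixed time between Day 15 and Day 29. The instructions in Tables 10 and 11 start only when a raised value has been found.

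A reader might infer more in three ways. The documents do not support any of them.

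- **That the exception is defective because it has no end criterion.** The diarrhea exception does name one ("Grade 3 diarrhea that has resolved to grade" 2 or less), as does the one for nausea and vomiting. But the limits for fatigue, neutropenia and thrombocytopenia also rest on duration alone, so hyperglycemia is not an outlier. Whether Grade 3 continues while newly started insulin continues is a definition the sponsor could usefully add. A Day 22 glucose would not settle it.
- **That Section 6.2 contradicts the glucose rules.** Section 6.2 asks for recovery to Grade 1 or less "or baseline before restarting study treatment", while 6.1.1 allows dosing on the glucose value ("Copanlisib should be administered if pre-glucose level is <160 mg/dL for fasting"). Section 6.3.1.1 is the specific rule for hyperglycemia, and Section 6.3 directs investigators to its algorithms, which largely settles dosing.
- **That the decision to advance to Part 2 is biased by a known amount.** The visible text gives neither the Part 1 size nor the share of patients with prolonged hyperglycemia, so no such figure can be derived.

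**Conclusion.** The point holds as a gap in scheduled monitoring. In the DLT window, the last scheduled glucose comes before the third infusion, and the next is 14 days later (10 to 18), against a 7-day limit. Hyperglycemia that persists or appears after that infusion can be missed or poorly dated. Unscheduled testing will often prevent this, so it is a low-cost improvement to consider rather than a flaw in the design. No frequency of misclassification and no effect on ORR is claimed.

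The conclusion assumes that the visible Appendix A is the full glucose schedule and that visits keep to their windows. Text is missing around Sections 5.2, 6.1, 6.1.1, 6.2 and 8, and it could contain further rules, such as an infusion-day glucose schedule. Same-day readings alone would not cover the days after Day 15.

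**What to change.** Add plasma glucose, fasting where possible, to the existing Cycle 1 Day 22 draw, by amending either the glucose row with footnote v or the chemistry list in footnote p. The nominal gap falls from 14 to 7 days (3 to 11 with windows). The cost is one extra analyte and a request to fast before a visit that already takes place. No new visit, blood draw or patient is needed.

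As an optional clarification, Section 3.2 and the synopsis could state whether Grade 3 hyperglycemia continues for as long as newly started insulin continues. The sponsor should choose the rule. If the end point is glucose-based, it should require sustained control: a single acceptable reading after insulin could close an episode that then recurs, and so under-count DLTs.

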APPENDIX B: RECIST V1.1

Measurability of Tumor

Tumor lesions/lymph nodes will be categorized as measurable or non-measurable. Measurable disease is defined by the presence of at least 1 measurable lesion.

Measurable

Tumor lesions: Measured in at least 1 dimension (longest diameter in the plane of measurement is to be recorded) with a minimum size of:

- 10 mm by CT or MRI scan (slice thickness \leq 5 mm)
- 10 mm caliper measurement by clinical examination (non-measurable lesions if cannot be accurately measured with calipers)
- 20 mm by chest x-ray.

Malignant lymph nodes: To be considered pathologically enlarged and measurable, a lymph node must be \geq 15 mm in short axis when assessed by CT scan (CT scan thickness recommended to be \leq 5 mm).

Non-measurable

All other lesions, including small lesions (longest diameter $<$ 10 mm or pathological lymph nodes with \geq 10 to $<$ 15 mm short axis) as well as truly non-measurable lesions. Lesions considered truly non-measurable include: leptomeningeal disease, ascites, pleural/pericardial effusions, lymphangitis cutis/pulmonis, inflammatory breast disease, lymphangitis involvement of skin or lung, abdominal masses/abdominal organomegaly identified by physical examination that is not measurable by reproducible imaging techniques.

Special Considerations for Lesion Measurability

Bone lesions:

- Bone scan, PET scan, or plain films are not considered adequate imaging techniques to measure bone lesions.
- Lytic bone lesions or mixed lytic-blastic lesions, with identifiable soft tissue components, that can be evaluated by cross sectional imaging techniques suchas CT or MRI, can be considered measurable lesions if the soft tissue component meets the definition of measurability.
- Blastic bone lesions are non-measurable.

Cystic lesions:

- Simple cysts should not be considered as malignant lesions (neither measurable nor non-measurable)
- Cystic lesions thought to represent cystic metastases can be considered as measurable lesions, if they meet the definition of measurability. If non-cystic lesions are presented in the same patients, these are preferred for selection as target lesions.

Proprietary Information of MD Anderson

Protocol 2020-1241

19 October 2022

Lesions with Prior Local Treatment:

- Tumor lesions situated at a previously irradiated area, or in an area subjected to other locoregional therapy, are non-measurable unless there has been demonstrated progression in the lesion.

Baseline Documentation of Target and Non-Target Lesions

Target Lesions

When more than 1 measurable lesion is present at baseline, all lesions up to a maximum of 5 lesions total (and a maximum of 2 lesions per organ), representative of all involved organs, should be identified as target lesions and will be recorded and measured at baseline. Non-nodal target lesions should be selected based on their size (lesions with the longest diameter), be representative of all involved organs, and should be able to be reproduced in repeated measurements. Measurable lymph nodes are target lesions if they meet the criteria of a short axis of ≥ 15 mm by CT scan. All measurements are to be recorded in the eCRF in millimeters (or decimal fractions of centimeters [cm]).

Non-Target Lesions

All other lesions (or sites of disease) are identified as non-target lesions (chosen based on their representativeness of involved organs and the ability to be reproduced in repeated measurements) and should be recorded at baseline. Measurement of these lesions are not required but should be followed as "present," "absent," or in rare cases "unequivocal progression." In addition, it is possible to record multiple non-target lesions involving the same organ as a single item on the eCRF (for example, multiple liver metastases recorded as 1 liver lesion).

Lymph nodes with short axis ≥ 10 mm but < 15 mm should be considered non-target lesions. Nodes that have a short axis < 10 mm are considered non-pathological and are not recorded or followed.

Response Criteria

Evaluation of Target Lesions

Completed Response (CR): Disappearance of all target lesions. Any pathological lymph nodes (whether target or non-target) must have reduction in short axis to < 10 mm. Tumor marker results must have normalized.

Partial Response (PR): At least a 30% decrease in the sum of diameter of target lesions, taking as reference the baseline sum diameters.

Progressive Disease (PD): At least a 20% increase in the sum of the diameters of target lesions, taking as reference the smallest sum on study (including the baseline sum if that is the smallest). In addition to the relative increase of 20%, the sum must also demonstrate an absolute increase of at least 5 mm.

The appearance of 1 or more new lesions is also considered progression.

For equivocal findings of progression (e.g., very small and uncertain new lesions; cystic changes or necrosis in existing lesions), treatment may continue until the next scheduled assessment. If at the next scheduled assessment, progression is confirmed, the date of progression should be the earlier date when

Proprietary Information of MD Anderson

Protocol 2020-1241

19 October 2022

progression was suspected.

Stable Disease (SD): Neither sufficient shrinkage to qualify for PR, nor sufficient increase to qualify for PD, taking as reference the smallest sum diameters while on study.

Not Evaluable (NE): When an incomplete radiographical assessment of target lesions is performed or there is a change in the method of measurement from baseline that impacts the ability to make a reliable evaluation of response.

Evaluation of Non-Target Lesions

Complete Response: Disappearance of all non-target lesions and normalization of tumor marker level. All lymph nodes must be non-pathological or normal in size (<10 mm short axis).

Non-CR/Non-PD: Persistence of 1 or more non-target lesions and/or maintenance of tumor marker level above the normal limits.

PD: Unequivocal progression of existing non-target lesions. The appearance of 1 or more new lesions is also considered progression.

NE: When a change in method of measurement from baseline occurs and impacts the ability to make a reliable evaluation of response.

Evaluation of Best Overall Response

The best overall response (BOR) is the best response recorded from the start of the study treatment until the earliest of objective progression or initiation of new anticancer therapy, taking into account any requirement for confirmation. The patient's BOR assignment will depend on the findings of both target and non-target disease and will also take into consideration the appearance of new lesions. The BOR will be calculated via an algorithm using the assessment responses provided by the investigator over the course of the study.

Time Point Response

It is assumed that at each protocol-specified time point, a response assessment occurs. (When no imaging/measurement is conducted/made at all at a particular time point, the patient is NE at that time point.) **Table 21** provides a summary of the overall response status calculation at each time point for patients who have measurable disease at baseline.

Table 21: Time Point Response: Patients with Target (\pm Non-target) Disease

Target Lesions	Non-Target Lesions	New Lesions	Overall Response
CR	CR	No	CR
CR	Non-CR/non-PD	No	PR
CR	Not evaluated	No	PR
PR	Non-PD or not all evaluated	No	PR
SD	Non-PD or not all evaluated	No	SD
Not all evaluated	Non-PD	No	NE
PD	Any	Yes or No	PD
Any	PD	Yes or No	PD

Proprietary Information of MD Anderson

Protocol 2020-1241

19 October 2022

Any	Any	Yes	PD
CR = complete response; PR = partial response; SD = stable disease; PD = progressive disease; NE = not evaluable.			

Confirmatory Measurement/Duration of Response

Confirmation

To be assigned a status of PR/CR, changes in tumor measurements must be confirmed by repeat assessments that should be performed 4 weeks (± 3 days) after the criteria for response are first met. To confirm a response of CR, a full assessment of all target and non-target lesions that were present at baseline must occur, including those measured by bone scan. To confirm a PR or SD, a full assessment of target lesions that were present at baseline must occur; assessment of non-target lesions is not required.

Duration of Overall Response

The duration of overall response is measured from the time measurement criteria are first met for CR or PR (whichever is first recorded) until the first date that disease is recurrent or objective progression is observed (taking as reference for PD the smallest measurements recorded on study).

The duration of overall CR is measured from the time measurement criteria are first met for CR until the first date that recurrent disease is objectively documented.

Duration of Stable Disease

SD is measured from the start of the treatment until the criteria for objective progression are met, taking as reference the smallest sum on study (if the baseline sum is the smallest, that is the reference for calculation of PD).

Proprietary Information of MD Anderson

Protocol 2020-1241

19 October 2022

